The primary analysis will compare the estimated endpoint of the primary outcome (WHO-5) between UP and dCBT conditions post treatment (19 weeks from allocation) adjusted for baseline WHO-5 values, variables predictive for missing data, and stratification variables (i.e. site (Copenhagen, Risskov, Slagelse) and diagnosis (depression, social anxiety disorder, panic disorder/agoraphobia)), fitting treatment (UP or dCBT) as a fixed effects factor.

We will use a one-sided 97.5% CI interval approach to test non-inferiority between conditions. The one-sided 97,5% CI for the between group difference point estimate post treatment will be calculated. Non-inferiority of UP compared to dCBT will be accepted if the lower bound of the 97,5% CI lies within the prespecified non-inferiority margin of – 9 WHO points (see Figure 1). If non-inferiority is accepted, we will use a closed testing procedure to test for superiority of UP over dCBT (i.e. lower bound of the 97,5% CI lies above 0).

The model will be fitted using a multilevel, mixed linear regression model, which allow us to use all 16 WHO-5 outcomes and handle missing data within the model. We will use stratification variables (i.e. site and diagnosis) and baseline outcome variables and treatment as fixed factors. We will apply an unstructured covariance matrix to the random effects in the model. If the model does not converge, we will apply other covariance matrixes (i.e. autoregressive, heterogeneous, compound symmetry, etc.) to the model and choose the covariance matrix with the best fit according to the Akaike Information Criterion. Note: During the blind review of data it turned out that, due to the imputation method used, we were not able to run the analysis applying a unstructured covariance matrix to the random effects in the model as planned Using the Akaike Information Criterion, the autoregressive, 4th order (AR4) covariance matrix,

showed the best fit with the data. Accordingly, the multilevel, mixed linear regression model were run applying the AR4 covariance matrix to the random effects in the model.

Secondary analyses

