For secondary analyses we will use ANCOVA to test for non-inferiority between treatment conditions post treatment. Effect sizes (Cohens *d*) for pre-post differences between and within treatment conditions will be calculated. Following conventions (Cohen, 1988) statistically significant effect sizes ≤ 0.2 will be considered not clinically relevant and for this study a non-inferior difference between conditions.

All analyses will be run allowing for adjustment for stratification variables (i.e. site and diagnosis), and baseline values.

The clinically meaningfulness of results of study will be evaluated calculating numbers and odds ratio for responders and remitted patients using binary logistic regression. 'Responders' are defined as patients receiving a clinically meaningful change in primary outcome, that is ≥ 10 WHO-5 points 'Remission' is defined as patients no longer meeting diagnostic criteria for their primary DSM-5-diagnosis evaluated with the MINI Neuropsychiatric Interview (MINI)²³ 19 weeks after assessment. As an explorative analysis, we will also calculate numbers and odds ratio for patients who no longer met diagnostic criteria for any emotional disorder posttreatment.

Sensitivity analyses

We will run sensitivity analyses for the primary outcome using different definitions of the PP population, depending on how many therapy sessions they attended (i.e. 6, 10 sessions) and using the full ITT-population. Further, we will run a sensitivity analysis without imputed data to assess the potential impact of imputation on the trial findings and assess the impact of missingness by loading the primary analysis using an extreme scenario countering our hypothesis (i.e. imputing the data based on values from the 10% and 90% fractile population). Finally, we will assess the impact of nesting patients in therapy groups by adding therapy group as a random factor. As this analysis might unblind the analyst, this analysis is run after deciphering the blinding.

Additional analyses

Analysis of primary and secondary outcomes will be repeated exploratory at six months follow up.

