Adverse events will be listed by group and type of event: (a) Minor adverse events will be reported as number of patients encountering any of these: increasing current medication more than one standard dose step; using according-to-need medication for more than two weeks; increasing current medication to entail more than four types of psychotropic medications; new prescription of supplementary medication (accepted at inclusion); changing previously prescribed antidepressant to another type. (b) Major adverse events will be reported as number of events: New prescription of medication (not accepted at inclusion); contacting psychiatric emergency due to self-injury; suicide attempt without hospitalization; drop-out of therapy due to experienced lack of effect or deterioration. (c) Critical adverse events will be reported as number of events: psychiatric hospitalization due to deterioration or suicide attempt; somatic hospitalization due to self-injury or suicide attempt; referral to electroshock treatment; suicide.

Model checking and validation

We will check the robustness of models by examining residuals.

Handling of missing data and blinding

Data entry is performed by the data manager and research assistants according to the main study protocol. We will undertake a blinded analysis of missing data and outliers to evaluate how to deal with missing data and outliers, and to explore possible predictors of missing data which should be controlled for in the primary and secondary analyses. The analysis of the primary and secondary outcomes will be conducted with the treatment allocation blinded. In the data extraction for the primary analysis, the intervention type is concealed. The intervention and control arm will randomly be coded as '1' and '2'. Deciphering will not be done before all analyses at post-treatment have been performed, and conclusions for the primary outcome has been formulated.

For this analysis plan, we define missing data as those patients with the absence of data at follow-up for one or more outcomes. Data are assumed to be missing at random.

In the primary analysis, the mixed linear regression model handles missing data by full information maximum likelihood, except for the baseline value of WHO-5. Missing baseline WHO-5 values will be handled by multiple imputation with chained equations (m=100) using stratification variables, post-baseline values and variables predicting missing baseline WHO-5 as predictors in the imputation model.

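### The confidence interval that decides non-inferiority and superiority ignores therapy groups, and the clustered model is run only after the primary conclusion is written

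*SAP*

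**What the plan says.** The SAP compares group UP with group dCBT (Inferential analyses). Under Primary analysis, the deciding model is a mixed regression of the 16 WHO-5 scores. Its listed terms include no therapy group: "We will use stratification variables (i.e. site and diagnosis) and baseline outcome variables and treatment as fixed factors". The multilevel structure is occasions within patients, and the AR4 covariance finally adopted describes correlation over occasions. The lower limit of the one-sided 97.5% interval is compared with -9, and the same limit then serves a second claim: "If non-inferiority is accepted, we will use a closed testing procedure to test for superiority of UP over dCBT".

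Therapy group appears only under Sensitivity analyses: "Finally, we will assess the impact of nesting patients in therapy groups by adding therapy group as a random factor". The timing and its reason follow: "As this analysis might unblind the analyst, this analysis is run after deciphering the blinding".

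Handling of missing data and blinding sets the general order of work. It states: "The analysis of the primary and secondary outcomes will be conducted with the treatment allocation blinded". On breaking the code it states: "Deciphering will not be done before all analyses at post-treatment have been performed, and conclusions for the primary outcome has been formulated".

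**The concern.** Patients who share a therapy group share therapists, sessions and one another, so their outcomes may be correlated. Each group delivers only one treatment, so any positive residual correlation adds variance to the treatment contrast. A model without the group level leaves that variance out of the standard error. The lower limit then clears -9, and afterwards 0, too easily. This is the error that the SAP's discussion of the analysis population tries to avoid: falsely concluding non-inferiority.

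The SAP does plan a clustered model, so the fault lies in its rank and timing. A clustered lower limit below -9 would come to light only after non-inferiority had been concluded, and the SAP does not say what would follow.

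A lesser point: the secondary ANCOVAs, which also test non-inferiority, and the responder and remission logistic models have no clustering adjustment. The SAP does say that the secondary analyses focus on estimation.

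**Working it through.** **Order of work.** Handling of missing data and blinding puts all post-treatment analyses and the primary conclusion before deciphering. Sensitivity analyses puts one post-treatment analysis of the primary outcome after deciphering. Taken literally, both cannot be followed. Under either reading of the conflict, the clustered result as scheduled comes after the conclusion.

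**Inputs from the SAP.** Margin -9, one-sided alpha 0.025 (z = 1.96), endpoint SD 20.44, 208 patients required (204 completers also stated).

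**Assumed, because the SAP gives no figure.** m = 5 to 8 analysed patients per therapy group; residual ICC 0 to 0.10 after baseline WHO-5, site and diagnosis; baseline-endpoint correlation r = 0.3 to 0.5.

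**The SAP's own sample size.** 4 × (1.96 + 1.2816)² × 20.44² / 9² = 216.8, or 109 per arm and 218 in total, not 208. That is a separate issue and is not counted here; 208 is used as stated.

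**Step 1: error of the unclustered rule.** Design effect DE = 1 + (m - 1) × ICC. True one-sided error = Φ(-1.96/√DE). Shortfall in interval width = 1 - 1/√DE. Neither depends on SD, sample size or r.

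| ICC | DE (m = 5 to 8) | True one-sided error | Interval too narrow by |
|---|---|---|---|
| 0 | 1.00 | 2.5% | 0% |
| 0.01 | 1.04-1.07 | 2.7%-2.9% | 2%-3% |
| 0.05 | 1.20-1.35 | 3.7%-4.6% | 9%-14% |
| 0.10 | 1.40-1.70 | 4.9%-6.6% | 16%-23% |

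**Step 2: where the decision changes.** SE = 20.44 × √(1 - r²) × √(4/208) = 2.704 (r = 0.3) or 2.455 (r = 0.5). The unclustered test declares non-inferiority when the observed difference exceeds -9 + 1.96 × SE = -3.70 or -4.19. With clustering at ICC 0.05 it must exceed -9 + 1.96 × SE × √DE:

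- r = 0.3: -3.19 (m = 5) to -2.84 (m = 8)
- r = 0.5: -3.73 (m = 5) to -3.41 (m = 8)

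**Step 3: how often the two models disagree at a true difference of 0.** The unclustered test passes with probability Φ((9/SE - 1.96)/√DE), and the clustered test with Φ(9/(SE√DE) - 1.96). At ICC 0.05:

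| r | m | Unclustered | Clustered | Difference |
|---|---|---|---|---|
| 0.3 | 5 | 0.894 | 0.860 | 3.5% |
| 0.3 | 8 | 0.881 | 0.817 | 6.3% |
| 0.5 | 5 | 0.940 | 0.917 | 2.3% |
| 0.5 | 8 | 0.929 | 0.884 | 4.5% |

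The same calculation gives 0.4%-1.1% at ICC 0.01 and 5%-13% at ICC 0.10. With 204 patients, thresholds move by about 0.05 and these percentages by at most 0.3 points.

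**Step 4: simulation.** Setting: baseline-adjusted endpoint, r = 0.3, true difference -9, 26 to 42 groups, 20,000 trials per setting.

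- Unclustered ANCOVA error: 2.5% at ICC 0, 2.6%-3.0% at 0.01, 3.7%-4.4% at 0.05, 5.0%-6.9% at 0.10.
- REML random group intercept with groups-minus-2 degrees of freedom: 1.7%-2.6% in every setting.
- Cluster-robust standard errors with the same degrees of freedom: 2.5%-2.9%.

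In further runs at a true difference of 0, disagreement between the two models was 4%-10% at ICC 0.05. It was 2%-4% at ICC 0, which is the cost of estimating the group variance. The simulation covers one endpoint, not the AR4 repeated-measures model or the 100 imputations.

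**The case against.** The SAP pre-specifies the clustered model and gives an honest reason for deferring it: group membership can reveal the arm. That reason is sound, since even recoded group labels may be betrayed by a group's diagnostic mix. It explains the order of work, but it does not make an unclustered interval valid, and the blind can be protected in other ways.

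Sensitivity analyses seldom carry decision rules, and the SAP gives none for its others. That is true. This one differs because it tests whether the standard error behind the decision is right, not whether the answer holds in another population or under other missing-data assumptions.

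The conflict over timing can be read as a general rule with a stated exception, and one clause would cure it. That is fair, and the conflict adds little to the weight of the point.

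The size rests wholly on assumed values, and site and diagnosis may absorb part of the between-group variance. At ICC 0.01 the error is close to nominal. This stands: the direction is known for any positive ICC, the size is not.

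Finally, the AR4 model was already run in the blind review, after the planned covariance proved unworkable with the imputation. A further level may have convergence trouble, and replacing a model already fitted carries some cost in credibility. Both are reasons for a stated fallback and for making the change before the blind is broken.

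**Conclusion.** The concern holds and should be fixed. That the deciding model lacks a therapy-group level, that the clustered model cannot inform the primary conclusion, and that no rule covers disagreement all follow from the SAP without any assumed figure. The protocol was not available, but the SAP states its own decision rule without clustering.

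The consequence is conditional on the residual ICC. At zero there is no fault in the interval. At 0.05 with 5 to 8 patients per group, the true error is roughly one and a half to nearly two times the nominal 2.5%, and observed differences between about -4 and -3 could pass one model and fail the other. Any precision gained from the session scores is not included in those thresholds.

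**What to change.** Put therapy group into the primary model as a random effect with small-sample degrees of freedom, for example REML with Satterthwaite pooled over the imputations, and amend the full-information-maximum-likelihood wording to match. Name a fallback for non-convergence: cluster-robust standard errors by therapy group with a small-sample correction. Base the decisions at -9 and 0 on that interval and keep the unclustered model as the sensitivity analysis.

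If the unclustered model must stay primary, state at least that each claim also requires the clustered lower limit to clear the same bound, and that the conclusion is written after both results are in.

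To keep the blind, let a person independent of the interpreting analyst, or a pre-specified script, fit the clustered model. The same person or script should do the two tasks that expose its details: the step to "choose the covariance matrix with the best fit according to the Akaike Information Criterion" and the check described as "We will check the robustness of models by examining residuals". Only arm-coded results go to the analyst until the conclusion is written. Reconcile Sensitivity analyses with Handling of missing data and blinding on the timing. Apply the same adjustment to the secondary ANCOVAs and the logistic models.

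The cost is wording, programming, a convergence check and one independent person or script. The Introduction leaves the SAP open to adjustment until the blind is broken. Power falls:

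- At ICC 0.05 the interval widens by 10%-16%. Power by formula goes from 88%-94% to 82%-92%. Simulated power with the random group effect is lower, at 78%-85% (r = 0.3) and 85%-90% (r = 0.5), against 88%-90% and 93%-94% unclustered.
- At ICC 0, simulated power still goes from 91% to 87%-89% (r = 0.3) or from 95% to 93%-94% (r = 0.5), because the group variance has to be estimated.

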Apart from the main objective, we investigate the effects of the UP on emotion regulation, the role of possible mediators and moderators on outcome, as well as qualitative data on patients' and therapists' experience of psychotherapy. These analyses are specified elsewhere.

Study methods

Design

Please see study protocol (Arnfred et al., 2017)⁷ or www.clinicaltrials.gov (Identifier: NCT02954731).

Randomization

Please see study protocol (Arnfred et al., 2017)⁷.

Sample size

Please see study protocol (Arnfred et al., 2017)⁷.

Correction: In the study protocol we wrote that alpha was set to 5% resulting in a 95% one-sided confidence interval (CI). Following Trial guidelines^{1,8}, the alpha should be 0.025 resulting in a 97.5% one-sided CI. Further, standard deviation (SD) endpoint WHO-5 was reported to be 17.4 WHO-5 points. As reported in Reinholt et al. (2017)⁹ the correct WHO-5 endpoint SD is 20.44. Using these corrected values, then a sample size of 208 patients are required to be 90% sure that the lower limit of a one-sided 97.5% confidence interval (or equivalently a 95% two-sided confidence interval) will be above the non-inferiority limit of -9 WHO-points.

Due to an unexpected, high attrition rate within the first year of inclusion, we decided to adjust sample size calculations by increasing the number of included patients from in total 248 patients to in total 320 patients to get 204 participants completing the treatment as needed for the primary analysis based on our initial sample size calculations. The revised sample size calculation is documented in an amendment to the protocol at www.clinicaltrials.gov (Identifier: NCT02954731).

Timing of outcome assessments

Baseline characteristics will be assessed at the time of inclusion. Outcome measures will be assessed pre-treatment (up to two weeks before start of intervention), post treatment (week 19-21 after allocation), and at six months follow-up (45-47 weeks after allocation). The primary outcome (WHO-5) is further assessed at the beginning of each therapy session (14 sessions).

Timing of final analysis

Primary and secondary outcomes are analyzed post treatment and exploratively repeated at six months follow-up.

Statistical principles

Data presentation

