In the secondary analyses, missing data will be handled by multiple imputations with chained equations (m=100) using baseline values of the scales in question, variables predicting missing data, and stratification variables, as auxiliary variables in the imputation models. In cases where other scales are theoretically strongly correlated to the missing data, these scales will also be used as auxiliary variables in the imputation models.

Missing data within a scale less than 25% will be handled by single imputation of mean-scores of the scale. Missingness above 25% within a scale will lead to missing value at scale level and be imputed as described above.

Statistical software

All analyses will be undertaken in SPSS, version 25 and Stata, version 15.^{26,27}

[name]., PhD-fellow, Mental Health Center of Copenhagen, Copenhagen University Hospital, Copenhagen, Denmark

16.8.15

Date

Signature

[name], MSc., statistical consultant, Copenhagen Research Center for Mental Health – CORE, Mental Health Center Copenhagen, Copenhagen University Hospital, Copenhagen, Denmark

Date

Signature

[name] [name]., Post doc, Mental Health Center of Copenhagen, Copenhagen University Hospital, Copenhagen, Denmark

16/08 - 2019

[name]

Date

Signature

[figure not shown]
Principal Investigator [name] [name], PhD, MSc; DMSc, Professor, Psychiatry West, Slagelse, Region Zealand Mental Health Service & Department of Clinical Medicine, Copenhagen University, Denmark

19/8 2019

[Handwritten Signature]

Date

Signature

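### The imputation models for baseline WHO-5 and for the secondary endpoints omit treatment arm, which shrinks any true difference between arms; the size depends on missingness that the SAP does not state

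*SAP*

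**What the plan says.** All references are to the SAP.

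- **Primary outcome, Handling of missing data and blinding.** Post-baseline WHO-5 is left to full information maximum likelihood. Missing baseline WHO-5 is filled in by chained equations with 100 imputations, "using stratification variables, post-baseline values and variables predicting missing baseline WHO-5 as predictors in the imputation model". The stratification variables are site and diagnosis, so arm is not among the listed predictors.
- **Secondary outcomes, same section.** Here the missing endpoints themselves are imputed, "using baseline values of the scales in question, variables predicting missing data, and stratification variables, as auxiliary variables in the imputation models". Other scales may be added where a strong correlation is expected on theoretical grounds. Arm is again absent.
- **Primary analysis.** The comparison is "adjusted for baseline WHO-5 values, variables predictive for missing data, and stratification variables", "fitting treatment (UP or dCBT) as a fixed effects factor". It is a repeated-measures model "which allow us to use all 16 WHO-5 outcomes and handle missing data within the model": one before treatment, 14 at sessions and one after treatment, so 15 are post-baseline. The section also reports that the imputation method prevented the planned unstructured covariance, and that AR4 was then chosen by AIC.
- **Secondary analyses.** The arms are compared by ANCOVA.
- **Sensitivity analyses.** The primary outcome is to be re-analysed without imputed data.
- **Blinding.** The analyst works with arms randomly coded 1 and 2.

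**The concern.** An imputation model should contain every variable of the analysis model, above all the one whose coefficient is to be estimated. Here it is left out, while the outcomes that carry its effect are used as predictors.

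Suppose UP is truly worse. UP patients with a missing baseline then have low later scores. A model without arm reads these as a sign of low baseline and imputes too low a value; in the dCBT arm it imputes too high a value. Adjusting for this artificial baseline imbalance removes part of the real deficit. For the secondary endpoints the route is more direct: a patient whose endpoint is imputed without arm contributes no arm difference beyond what the other predictors convey.

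At stake is the error rate at the -9 margin, where shrinkage toward zero makes it easier to accept non-inferiority. The section on the analysis population itself warns about choices that make the arms look alike.

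**Working it through.** The SAP gives no figure on this point, neither a rate of missing baselines nor a bias, so there is nothing to reproduce first.

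**Inputs from the SAP.** Endpoint SD 20.44; margin -9; 208 patients, taken as 104 per arm; 15 post-baseline scores; one-sided level from "the alpha should be 0.025 resulting in a 97.5% one-sided CI".

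**Assumptions.** True difference τ = -9; share of missing baselines m from 5% to 30%, missing completely at random; the correlations shown. ANCOVA at the last visit stands in for the mixed model.

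**1. One post-treatment score as predictor.** Let r be the baseline-to-post correlation, with equal SDs. Without arm, the slope of baseline on the post score is about r, so imputed baselines differ between arms by about r·τ. Over all patients the false imbalance is m·r·τ, and adjustment with slope r removes m·r²·τ. The shrinkage is therefore about 9·m·r² points.

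- r = 0.5: 9 × 0.10 × 0.25 = 0.23 at 10% missing; 0.45 at 20%; 0.68 at 30%.
- r = 0.7: 9 × 0.10 × 0.49 = 0.44 at 10%; 0.88 at 20%; 1.32 at 30%.

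Simulation with 400,000 patients gives 0.20, 0.42 and 0.62 for r = 0.5, and 0.43, 0.86 and 1.34 for r = 0.7 (with-arm minus without-arm imputation). With arm included, the estimate is about -8.9 to -9.1.

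**2. All 15 post-baseline scores, as planned.** Shrinkage in points, 400,000 simulated patients:

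| Correlation between scores | Arm effect | 5% | 10% | 20% | 30% |
|---|---|---|---|---|---|
| Serial, 0.9 per step | grows linearly | 0.01 | 0.01 | 0.02 | 0.03 |
| Serial, 0.9 per step | full from session 1 | 0.08 | 0.15 | 0.30 | 0.44 |
| Equal, 0.5 | grows linearly | 0.09 | 0.19 | 0.38 | 0.57 |
| Equal, 0.5 | full from session 1 | 0.19 | 0.36 | 0.77 | 1.14 |
| Equal, 0.7 | grows linearly | 0.13 | 0.28 | 0.54 | 0.76 |
| Equal, 0.7 | full from session 1 | 0.29 | 0.58 | 1.15 | 1.71 |

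A hand check for equal correlation ρ and an immediate effect: shrinkage ≈ 9·m·ρ·B, with B = ρ / (ρ + (1-ρ)/15 + τ²/(4·SD²)). The last term is 81 / (4 × 417.8) = 0.048. For ρ = 0.7, B = 0.7 / (0.7 + 0.02 + 0.048) = 0.91, and at 30% missing 9 × 0.3 × 0.7 × 0.91 = 1.72, in line with the table.

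**3. False acceptance of non-inferiority at a true -9.** One post score, 104 per arm, 20 imputations, Rubin's rules, 3,000 trials per cell; nominal 2.5%.

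| Missing | Without arm, r = 0.5 / 0.7 | With arm, r = 0.5 / 0.7 |
|---|---|---|
| 10% | 3.5% / 3.0% | 2.7% / 2.6% |
| 20% | 3.3% / 4.1% | 2.4% / 2.9% |
| 30% | 3.5% / 6.0% | 2.5% / 3.2% |

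The Monte Carlo standard error is about 0.3 to 0.4 percentage points, so the 10% row barely separates the two models.

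**4. Secondary endpoints.** If only the baseline of the same scale and the stratification variables predict the endpoint, imputed patients carry no arm difference and the estimate becomes d·(1-m). A true d of 0.25 falls to 0.25 × 0.8 = 0.20 at 20% imputed, which is the threshold that the SAP sets under Secondary analyses. If an observed scale correlated 0.7 and showing the same standardized effect is included, only about 0.3 of that share is lost: 0.25 × (1 - 0.3 × 0.2) = 0.235.

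**5. Direction.** Every expression above is proportional to the true difference, or nearly so. It vanishes at zero and changes sign with it.

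**The case against.** The best case against acting has four parts.

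- **Size.** The plan uses many early session scores. If neighbouring scores correlate most and the arms separate slowly, those early scores dominate the imputation and carry little arm effect, so the shrinkage is almost nil even at 30% missing. This stands, and is why no single figure can be given.
- **Missingness.** A reader might infer 20-30% missing baselines from the attrition that raised enrolment to 320 for 204 completers. The SAP does not support that: those figures concern completing treatment, whereas baseline is taken before it and the main population is patients with at least eight sessions. The report that imputation interfered with the covariance structure shows that it was used, not how much.
- **Direction.** A reader might also infer that the rule is anti-conservative whatever the truth and at any rate of missingness. It is not. Under the trial's own hypothesis of equal improvement there is no bias, and if UP is better the shrinkage works against the superiority step.
- **Existing safeguards.** The re-analysis without imputed data targets this step, because in the primary analysis only baseline is imputed. It can detect the problem but leaves the primary result as it is, and that paragraph is framed around the primary outcome, so the secondary endpoints are not covered. Arm could also enter as a predictor of missingness, but only by chance; the text does not provide for it.

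**Conclusion.** The point holds as a defect in the stated rule, with a size that the SAP does not determine. Followed as written, both imputation models shrink a true arm difference, and at the -9 margin this favours non-inferiority.

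For the primary outcome at a true -9, the shrinkage is about 0 to 0.5 points if 5-10% of baselines are missing (0.58 in the most extreme case tried), which is small beside a 9-point margin. If 20-30% are missing, it runs from near 0, with serially correlated scores and an effect that grows over sessions, to between 1 and 2 points with an immediate effect. For secondary endpoints, the share of endpoints imputed is roughly the ceiling, and the loss is smaller where an observed correlated scale carries the arm effect.

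These figures rest on assumed missingness and correlations, and on ANCOVA in place of the mixed model. They do not show that a non-inferiority conclusion from this trial would be wrong.

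**What to change.** In both imputation paragraphs under Handling of missing data and blinding, add the masked arm code (1/2) to the listed predictors, or state that imputation is done separately by arm. Report the number of missing baseline WHO-5 values by masked arm, so that the reader can judge the size. Keep the analysis without imputed data as a check.

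The cost is one more variable in the imputation code, a re-run of the imputations, and a repeat of the AIC choice of covariance structure reported under Primary analysis, since that choice was made with the imputation method already in use. The masked code is already needed for the analysis model, so nothing is unblinded.
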